12.5. Selecting and Marking Dimples

If all 4 quadrants (both buttocks and both thighs) meet entry criteria for a single subject, the thighs will be treated. No subject will have treatment in all 4 quadrants (both buttocks and both thighs) during this study.

Selection of dimples to be treated in the treatment areas (both buttocks or both thighs) is at the discretion of the investigator. Dimples must be well defined, evident when the subject is standing in a consistent, standardized relaxed pose (without the use of any manipulation such as skin pinching or muscle contraction), and suitable for treatment. Each subject will receive 3 treatment visits of study drug unless the treatment area is dimple-free at Day 22 and/or Day 43. A dimple-free buttock or thigh at Day 1 is precluded by the eligibility criteria. A dimple-free buttock or thigh at Day 22 and/or Day 43 does not preclude treatment of the contralateral buttock or thigh unless it is also dimple-free.

Detailed instructions for the marking and imaging of dimples will be provided in the 3-D Photography Manual.

12.6. CR-PCSS

The CR-PCSS - Buttock ([Appendix A](#)) and the CR-PCSS - Thigh ([Appendix B](#)) will be used to assess the severity of cellulite of both treatment areas at Screening (each buttock or each thigh independently). The scale is a 5-level photonumeric scale developed specifically for clinicians and used by the Investigator to assess the severity of the subject's cellulite in each buttock or thigh by live assessments. The ratings range from 0 (None) to 4 (Severe) with labels and descriptors to aid the Investigator in the assessments. This assessment should be made while the subject is in the standing position with relaxed gluteus muscles.

Investigators will be trained and qualified on the use of the CR-PCSS prior to assessing any subjects.

13. ASSESSMENT OF EFFICACY

13.1. 3-D Photography

Although 3-D photographs are not direct efficacy measurements, 3-D photography will be utilized in the assessment of treatment effect. The Investigator or qualified designee will photograph each treatment area (each buttock or each thigh) using a Sponsor-supplied standardized 3-D camera in a standardized manner. The subject will be standing for each photography session and will be wearing a standardized photographic garment as described in the 3-D Photography Manual. The Investigator or qualified designee will photograph each of the 2 treatment areas (2 buttocks or 2 thighs) while the subject is standing in a consistent, standardized relaxed pose.

On each treatment day (Day 1, Day 22, and Day 43), 3-D photographs will be taken before and after marking dimples and injection sites. At screening and all other study visit days, a single set of photographs will be taken. 3-D photographs will be taken prior to study drug dosing.

For 3-D photographic images taken on Days 4, 8, 15, 22, 43, and 71, a central assessor blinded to the treatment arm and study visit day will complete a 5-point Likert scale to gauge the level of aesthetic improvement achieved (from baseline) in each treatment area.

All de-identified photographs from this study are the property of Endo and may be utilized for clinical development, scientific communication, marketing, regulatory purposes, and/or legal applications as required/desired by Endo.

13.2. Hexsel Depression Depth Scale

The Hexsel Cellulite Severity Scale (Hexsel CSS) is a photonumeric scale that looks at 5 key morphologic features of cellulite: (A) number of evident depressions, (B) depth of depressions, (C) morphological appearance of skin surface alterations, (D) laxity, flaccidity or sagging of skin, and (E) current classification scale based on medical literature ([Hexsel et al, 2009](#); [Nürberger and Müller, 1978](#)). Each of these features is evaluated on a 4-point scale from a low of 0 to a high of 3. For this study, only (B) depth of depressions will be assessed.

The Investigator or qualified designee will independently use the Hexsel CSS (B) depth of depressions in assess the severity of EFP in each buttock or each thigh (see [Appendix C](#)). This

assessment should be made while the subject is in the standing position with relaxed gluteus muscles.

14. ASSESSMENT OF SAFETY

14.1. Definitions

14.1.1. Adverse Events

An AE is any unfavorable or unintended change in body structure (signs), body function (symptoms), laboratory result (eg, chemistry, ECG, X-ray, etc), or worsening of a pre-existing condition associated temporally with the use of the study medication whether or not considered related to the study medication. Adverse events will be captured once a subject has signed the informed consent. AEs include:

- Changes in the general condition of the subject
- Subjective symptoms offered by or elicited from the subject
- Objective signs observed by the Investigator or other study personnel
- All concurrent diseases that occur after the start of the study, including any change in severity or frequency of pre-existing disease
- All clinically relevant laboratory abnormalities or physical findings that occur during the study

A treatment-emergent AE (TEAE) is any condition that was not present prior to treatment with study medication but appeared following treatment, was present at treatment initiation but worsened during treatment, or was present at treatment initiation but resolved and then reappeared while the individual was on treatment (regardless of the intensity of the AE when the treatment was initiated).

All AEs, including both observed or volunteered problems, complaints, signs or symptoms must be recorded on the AE page of the eCRF, regardless of whether associated with the use of study medication. This would include AEs resulting from concurrent illness, reactions to concurrent medication use, or progression of disease states (excluding the disease under study). A condition present at baseline that worsens after initiation of study treatment will be captured as an AE; the onset date will be the date the event worsened. The AE should be recorded in standard medical terminology when possible.

14.1.2. Serious Adverse Events

A serious adverse event (SAE) is defined as an AE that:

- Results in death
- Is immediately life-threatening (there is an immediate risk of death from the AE as it occurred; this does not include an AE that had it occurred in a more serious form may have caused death)

- Results in or prolongs an inpatient hospitalization (Note: a hospitalization for elective or pre-planned surgery, procedure, or drug therapy does not constitute an SAE)
- Results in permanent or substantial disability (permanent or substantial disruption of one's ability to conduct normal life functions)
- Is a congenital anomaly/birth defect (in offspring of a subject using the study medication regardless of time to diagnosis)
- Is considered an important medical event

Important medical events are defined as events that, based upon appropriate medical judgment, may jeopardize the subject and may require medical or surgical intervention to prevent one of the other serious outcomes. Examples of important medical events include allergic bronchospasm requiring intensive treatment in an emergency room or at home, blood dyscrasias or convulsions that do not result in inpatient hospitalization, or the development of drug dependency or drug abuse.

14.2. Monitoring Adverse Events

At each study visit, subjects will be queried regarding any AEs that have occurred since the last study visit. Subjects will be asked to volunteer information concerning AEs with a non-leading question such as, "How do you feel?" Study center personnel will then record all pertinent information in the source documents and the eCRF. The study drug compliance record should also be reviewed to detect potential overdoses (intentional/unintentional).

14.3. Relationship to Study Drug

The degree of "relatedness" of the AE to the study medication must be described using the following scale:

- **Not related** indicates that the AE is definitely not related to the study medication.
- **Unlikely related** indicates that there are other, more likely causes and study medication is not suspected as a cause.
- **Possibly related** indicates that a direct cause and effect relationship between study medication and the AE has not been demonstrated, but there is evidence to suggest there is a reasonable possibility that the event was caused by the study medication.
- **Probably related** indicates that there is evidence suggesting a direct cause and effect relationship between the AE and the study medication.

It is the Sponsor's policy to consider "Probably related" and "Possibly related" causality assessments as positive causality. "Not related" and "Unlikely related" causality assessments are considered as negative causality.

Assessments will be recorded on the eCRF and must indicate clearly the relationship being assessed. For example, an AE that appears during a placebo run-in phase would be assessed with respect to the placebo treatment received and/or study procedures conducted during this phase. If the AE continued into an active treatment phase, the relationship would be assessed for the active treatment phase only if the AE worsened.

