9.2. Secondary Objective

The secondary objective of this study is to assess the safety of CCH when administered using different injection techniques in subjects with EFP.

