14.5. Reporting Adverse Events and Serious Adverse Events

14.5.1. Reporting Adverse Events

Throughout the study, AEs will be documented on the source document and on the appropriate page of the eCRF whether or not considered treatment-related. This includes any new signs, symptoms, injury or illness, including increased severity of previously existing signs, symptoms, injury, or illness. Conditions existing prior to screening will be recorded as part of the subject's medical history. The Investigator is responsible for assessing the relationship of AEs to the study medication; relationship will be classified as not related, unlikely related, possibly related, or probably related.

All AEs will be collected by the Investigator from the time of signing the informed consent through 28 days after the last dose of study medication; this includes any AEs that are ongoing at the time of completion/termination of the study. All ongoing AEs must be followed until resolution or for 28 days after the subject's last study visit, whichever comes first.

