### **3.6. Study Drug Administration**

Each subject will receive 24 injections for a total of 1.68 mg (0.84 mg per treatment area) at each treatment visit. The cumulative CCH dose will be 5.04 mg for each subject who completes the 3 treatment visits.

Each subject will receive study drug on Day 1, Day 22 and Day 43 (treatment visits) unless the treatment area is dimple-free at Treatment Visit 2 (Day 22) and/or Treatment Visit 3 (Day 43). A dimple-free buttock or thigh at Treatment Visit 1 (Day 1) is precluded by the eligibility criteria. A dimple-free buttock or thigh at Treatment Visit 2 (Day 22) and/or Treatment Visit 3 (Day 43) does not preclude treatment of the contralateral buttock or thigh unless it is also dimple-free.

The study drug, CCH, will be administered using 1 of 5 injection techniques. Each of the injection techniques are referred to as a treatment arm (I - V). Subjects will be sequentially assigned to a treatment arm at Day 1. Injection techniques differ from each other in, concentration of the CCH injectate, angle of injection, depth of injection, volume of injection and study drug administration at injection site.

At every treatment visit, irrespective of the treatment arm (injection technique) assigned, all eligible subjects will receive the same amount of study drug (CCH, 0.84mg) injected in each

assigned treatment area. All eligible subjects with dimples (in each buttock or thigh) that require treatment to improve the aesthetic appearance will receive full treatment course with CCH injections. Across all treatment arms, study drug will be administered subcutaneously while subject is in a prone position.

The injection volume and concentration for each treatment arm are outlined in [Table 2](#) below.

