#### **4.6.1.3. Relationship to Study Drug**

Causal relationship of AE with study drug will be classified by the Investigator and will be reported as follows:

- Not related
- Unlikely related
- Possibly related
- Probably related

Related adverse events are AEs with the relationship described by the investigator as “probably related” or “possibly related”. “Not related” or “Unlikely related” causality assessments are considered as negative causality.

Any missing relationship of an AE to study drug will be considered as related to study drug for the analyses, following worst case principle.

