### **7.8.2. Adverse Events**

All AE summary tables will include only TEAEs, unless otherwise specified.

AEs will be summarized by SOC and PT. A subject will only be counted once per SOC and PT.

For AEs by severity grade (mild, moderate, severe), if a subject has multiple events occurring in the same SOC or same PT, then the event with the maximum intensity (ie, severe) will be counted.

For AEs by relationship to study drug, if a subject has multiple events occurring in the same SOC or same PT, the event with the highest association (ie, related) to study drug will be summarized.

AEs will be presented in decreasing order of the incidences at SOC level and within each SOC, in decreasing order of the incidences at the PT level.

An overall summary of AE and AE related to study drug will be presented and will include:

- Total number of TEAEs reported
- Total number of TEAEs reported by severity
- Total number of AEs of special interest
- Subjects with any TEAE
- Subjects with any special interest AE
- Subjects with any serious TEAE
- Subjects with any severe TEAE

- Subjects with no severe TEAEs, but at least one moderate TEAE
- Subjects with no severe TEAEs, but at least one mild TEAE
- Subjects with any TEAEs leading to drug interruption/withdrawn
- Subjects with any TEAEs leading to study discontinuation
- Subjects with any TEAEs resulting in death

The following summary tables will be presented by SOC and PT:

- All TEAEs
- TEAEs by severity
- TEAEs by relationship to study drug
- All non-study drug related TEAEs
- All study drug related TEAEs
- Study drug related TEAEs by severity
- Serious TEAEs
- Serious study drug related TEAEs
- Duration of study drug related TEAEs (<14 days, 14 – 21 days and >21 days)
- TEAEs leading to drug interruption/withdrawn
- Study drug related TEAEs leading to drug interruption/withdrawn
- TEAEs leading to study discontinuation
- Study drug related TEAE leading to study discontinuation
- TEAEs resulting in death
- Study drug related TEAEs resulting in death
- AEs of special interest

Serious and most common non-serious TEAE by order of frequency (Most frequent, 2nd most frequent, and 3rd most frequent) will be summarized by PT. Most common non-serious AEs are any preferred term that at least 5% of the subjects reported at least once.

The following listings will be presented by subject:

- All AEs
- Serious AEs
- AEs resulting in drug interruption/withdrawn

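### The only adverse event duration table is limited to drug-related events, although causality is rated against the drug alone and the arms differ only in injection technique

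*Protocol*

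**What the plan says.** **Causality.** Protocol 14.3 says the relatedness "of the AE to the study medication must be described using the following scale", and all four levels are defined against the medication. *Unlikely related* "indicates that there are other, more likely causes and study medication is not suspected as a cause". It is grouped with *Not related*, and these "causality assessments are considered as negative causality". Protocol 14.5.1 sets the same task: "The Investigator is responsible for assessing the relationship of AEs to the study medication". SAP 4.6.1.3 repeats it: "Causal relationship of AE with study drug will be classified by the Investigator". Neither document gives a rating for the injection procedure. Protocol 14.3 names study procedures once, in an example about a placebo run-in, and this study has no such phase.

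**Arms.** SAP 3.6 states that, whatever the arm, "all eligible subjects will receive the same amount of study drug". The arms are five injection techniques. The secondary objective (Protocol 9.2) is to "assess the safety of CCH when administered using different injection techniques".

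**Tables.** SAP 7.8 splits safety summaries by arm and region. The SAP 7.8.2 list contains "Duration of study drug related TEAEs", in bands of under 14, 14 to 21 and over 21 days. No duration table covers all TEAEs. Protocol 17.6.4 plans no duration table, so this is the only one.

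**The concern.** The causality question is put to the component that all arms share, the drug and its dose. The component that varies, how the drug is delivered, has no place on the scale. If an investigator believes that a bruise or pain came from needle depth, repositioning or injected volume and does not suspect the drug, *Unlikely related* is an available answer. The event then drops out of every table restricted to related events.

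For duration this matters because nothing else in the planned tables takes its place. The bands line up with the 21-day treatment interval, and Protocol 8.4 relies on most events having resolved before the next treatment. Time to resolution is therefore a natural quantity to compare across techniques. As planned, which events enter that summary depends on an unblinded judgement (Protocol 12.4). It is made by the investigator, who also gives the injections (Protocol 12.3), at about 5 sites.

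**Working it through.** **Step 1. Is the dose really the same?** Inputs are from Protocol Table 1 and SAP Table 2: 0.07 mg per injection, 12 injections per area, 2 areas, 3 visits.
- Per area: 0.07 × 12 = 0.84 mg.
- Per visit: 0.84 × 2 = 1.68 mg.
- Cumulative: 1.68 × 3 = 5.04 mg.

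These reproduce the stated figures. Printed concentration × volume × 24 gives 1.656 mg (I to III), 1.692 mg (IV) and 1.728 mg (V). The differences from 1.68 mg are −1.4%, +0.7% and +2.9%, and they come from rounding the concentrations (0.07/0.3 = 0.2333; 0.07/1.5 = 0.0467; 0.07/1.2 = 0.0583 mg/mL). The premise of equal dose holds.

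**Step 2. What differs?** From Protocol Table 1 and Protocol 10.3.1 to 10.3.5:

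| Arm | Needle | Aliquots per injection | Concentration (mg/mL) | Volume per visit (mL) |
|---|---|---|---|---|
| I | 1/2 inch | 3 | 0.23 | 24 × 0.3 = 7.2 |
| II | 1/2 inch | 1 | 0.23 | 7.2 |
| III | 1 inch | 1 | 0.23 | 7.2 |
| IV | 1 inch | 5 | 0.047 | 24 × 1.5 = 36 |
| V | 1/2 inch | 4 | 0.060 | 24 × 1.2 = 28.8 |

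Volume differs up to 36/7.2 = 5-fold and concentration up to 0.23/0.047 = 4.9-fold. Technique therefore includes how concentrated the drug is locally, as well as needle mechanics.

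**Step 3. Which related-only tables have an all-cause partner in SAP 7.8.2?**

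| Related-only table | All-cause partner |
|---|---|
| All events | yes |
| By severity | yes |
| Serious | yes |
| Drug interruption or withdrawal | yes |
| Study discontinuation | yes |
| Death | yes |
| Duration | **no** |

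Six of seven have a partner; duration is the exception. SAP Table 12 derives duration for every AE (end date − start date + 1), so the restriction is not for want of data.

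**Step 4. How large could the effect be?** The documents give no share of events attributed to the procedure. Two assumptions give a range. Suppose a technique adds 20 percentage points to an event rate, with 12 subjects per arm (6 per region × 2 regions). Let m be the share of these extra subjects all of whose such events are rated negative. The difference in the all-TEAE table is 12 × 0.20 = 2.4 subjects. In a related-only table it is 2.4 × (1 − m):
- m = 0: 2.4
- m = 0.5: 1.2
- m = 1: 0

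The range runs from no effect to complete loss of the difference, and nothing in the documents narrows it.

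**The case against.** Much of the safety comparison does not depend on attribution. Protocol 17.6 summarises the proportion of subjects with each event by arm. SAP 7.8.2 tabulates all TEAEs, TEAEs by severity, by relationship, those not related, and AEs of special interest. SAP 7.8.7 compares bruise colour with normal skin at Days 4, 8 and 15 by area and arm, with no causality judgement. SAP 6.1 promises listings of all eCRF data and derived variables, so the duration of an unrelated event can be read there. All of this stands. It confines the point to one summary table and the wording of the scale.

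The backstops have limits for duration. The bruise analysis follows colour to Day 15 only, so it does not cover the later treatments, pain or nodules. SAP 3.17.3 attaches the special-interest label explicitly to remote bruising and hypersensitivity, and says only that local reactions are recorded. A listing is not a summary by arm.

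It is also fair that investigators may seldom use *Unlikely related* for a local reaction. That rating requires the drug not to be suspected, whereas *Possibly related* needs only a reasonable possibility. Protocol 8.3 lists injection site bruising and pain as treatment-related in Phase 2b, and Protocol 8.1.2 links most earlier events to local administration of CCH. Missing ratings default to related (SAP 4.6.1.3), though this does not touch an event actually rated *Unlikely related*. The effect may be small, but the scale does not say whether administration counts as the drug, so sites can read it differently.

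**Conclusion.** The point holds in a limited form. Causality is rated against study medication only, and the sole duration table admits only events rated related. Summarised durations by technique therefore depend on open-label attribution. This is a gap in completeness in a descriptive, exploratory study with 6 subjects per region per arm. No stated figure is wrong.

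A reader might infer three stronger things that the documents do not support:
- **That harm caused by a technique disappears from the safety comparison.** It does not; the all-cause tables and the bruise analysis retain it.
- **That the related-only tables are there to rank techniques, and would rank a more traumatic one as safer.** No section gives them that purpose. Local drug concentration is also part of technique, so rating against the drug is not beside the point.
- **That the bias can be sized from the Phase 2b bruising rate of 75.1%.** Protocol 8.3 reports this as a treatment-related rate, so attribution has already been applied. SAP 7.8.2 counts each subject at the highest association, so a share per bruise cannot be applied per subject. Any share would be invented.

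The conclusion rests on one assumption: that some investigators will attribute some local events to the injection and not suspect the drug. The wording permits this; how often it happens is unknown.

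**What to change.** 1. **SAP 7.8.2.** Produce the duration table, with the same three bands and by arm and region, on all TEAEs at the treated areas regardless of attribution. Use the AE duration in SAP Table 12. The related-only version can stay beside it. This needs no new data and can be done whatever the causality ratings already collected.
2. **Protocol 14.3 and 14.5.1 and SAP 4.6.1.3.** Word relatedness as related to study drug and/or its injection procedure. This helps only for ratings made under the new wording, so it should not delay the first change.

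The cost is one more table and a wording change. The downside is that stated related rates become slightly higher and less directly comparable with rates from studies that used the drug-only wording.
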